1. OBJECTIVES

1.1 Study Design

This will be an open label, multi-center, phase 0/II trial of abemaciclib (LY2835219) in participants with recurrent glioblastoma (GBM) at their first or second relapse. Patients must have documented evidence of CDKN2A/B loss and intact RB in previously obtained tumor tissue by exome sequencing, copy number analysis [e.g. array comparative genomic hybridization (CGH)] and/or IHC for RB prior to enrollment into the study.

In the phase 0 surgical arm (cohort 1), fifteen participants who require reoperation and have evidence of CDKN2A/B loss and intact RB from a prior tumor sample will receive a short preoperative course of abemaciclib for 10-14 days. Tissue will be used to investigate the ability of abemaciclib to pass through the blood brain barrier (BBB), achieve therapeutic concentrations in the tumor, and inhibit cellular proliferation in tumor tissue. Immunohistochemistry analysis for pRB, KI67, p21, and cleaved caspase 3 in tumor tissue obtained during the surgery as compared with tissue from a prior surgery will be used as a measure of decreased tumor cell proliferation and increased tumor cell death. In addition, as exploratory aims, we will perform functional biomarker analysis on live cells and patient derived cell lines and xenografts obtained from cohort 1 patients in order to determine their response to abemaciclib and investigate the associations between clinical outcomes and immunologic effects of abemaciclib. After surgery, cohort 1 participants will come off study treatment and pursue standard cancer treatments as per the treating physician's discretion.

The phase II treatment arm (cohort 2) will be comprised of 32 participants not requiring surgery. Participants will receive treatment with abemaciclib for each 28 day cycle (if participant tolerates first cycle of treatment well, abemaciclib may be increased for all subsequent cycles if the investigator determines that it is in the best interest of the patient). The primary endpoint is to determine the overall efficacy of abemaciclib as determined by six-month progression free survival (PFS6). Participants will remain on treatment until tumor progression, as long as there are no unacceptable toxicities. Responses will be assessed by clinical examinations every 4 weeks and MRI scans every 8 weeks. Responses determined using the new Response Assessment in Neuro-Oncology (RANO) criteria (Wen et al., 2010).

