5.2 Cohort 1—Surgery Arm

In Cohort 1, 15-20 eligible participants who require reoperation will be treated with abemaciclib for 10-14 days prior to surgery. The last dose should be on the day of surgery and taken 1-3 hours prior to surgery and tumor removal. Since participants in cohort 1 are undergoing PK testing, accurately recording the time of study drug administration on day of surgery and recording the time of tumor removal are especially important and required.

In general, pre-operative, operative, and post-operative evaluations will consist of standard clinical practice. Required evaluations and research samples are detailed in Section 10.

After surgery on study, cohort 1 participants will come off study treatment and pursue standard cancer treatments as per the treating physician's discretion. Participants who enrolled on the surgical cohort before the surgical cohort was converted into a Phase 0, who have already started post-surgical abemaciclib dosing, and are benefitting from post-surgical abemaciclib treatment may remain on abemaciclib at the discretion of their treating physician and the approval of the overall PI, [name]. These patients should instead follow the Study Calendar intended for Cohort 2 (nonsurgical) patients and their post-surgical C1D1 will represent C1D1 on the Cohort 2 study calendar.

Following registration, Cohort 1 pre-surgical Day 1 subjects should be evaluated for eligibility to treat based upon dose modification criteria outlined in Table 6.3 and not General Eligibility Criteria outlined here in Protocol Section 3; General Eligibility Criteria outlined here in Protocol Section 3 need only be met during screening for trial.

The goal is to have 15 eligible patients with adequate tissue for assessment of the primary objectives for this cohort. If sufficient tissue is not obtained for a patient enrolled in this cohort, the patient should continue treatment as originally intended and the clinical results reported. However, additional patients will be added to the cohort for the purpose of meeting the objectives related to tissue analysis. A maximum of 20 patients may be enrolled in this cohort. If the number of patients required to be replaced exceeds 5 consideration will be given to stopping enrollment to this cohort based on lack of feasibility.

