 - O TIL Density and TCR Overlap: We will evaluate whether next generation sequencing of the T cell receptor (TCR) repertoire within GBM tissue and blood can identify shared TCRs, which can then effectively track anti-tumor immune responses induced by abemaciclib. Genomic DNA will be isolated from fresh-frozen tumor (protocol surgery) and peripheral blood (immune monitoring timepoints) and subjected to next generation sequencing through the TCRVβ region to quantify TIL density and assess the overlap between tumor and peripheral blood. The TIL density and TCR overlap will then be correlated with clinical variables to identify potential biomarkers with prognostic and predictive value for outcomes (ORR, PFS, OS and toxicity). The TIL density and TCR overlap will be performed at Adaptive Biotechnologies (Seattle, WA). Investigators at the UCLA Brain Tumor Immunology Research Laboratory will perform analysis. Guidance on peripheral blood collection, processing and shipping is provided in Table 9.2 below.
 - o Immunological multiplex immunofluorescence (IF) measurements: a minimum of 10 FFPE unstained sections from the protocol surgery are to be submitted per Table 9.2 below. Multiplex IF will be performed to assess the proportion of tumor infiltrating lymphocytes (TIL) with PD-1 expression and delineation of PD-L1 expression on GFAP+ tumor cells versus myeloid cells (CD45+) within the tumor microenvironment.
 - Peripheral Blood Immunophenotyping: The absolute lymphocyte count and

proportion of specific lymphocyte subsets will be quantified at each time point. Using a mass cytometry (CyToF) antibody panel analysis, lymphocyte/leukocyte subsets, activation markers, and negative costimulatory molecules will be evaluated before and after administration of abemaciclib. Lineage markers for immune cell populations, activation markers, memory/antigen experience markers, and exhaustion markers will be stained with an established 24 antibody CyToF panel. Analysis will be done using CyToF Kit and Phenograph, and clusters subsequently downloaded as .fcs files for analysis using FloJo. CyToF analysis will be performed on PBMC obtained from Ficoll density gradient separation of whole blood. Blood draws for this testing will be done pre-treatment and on the day of surgery prior to dosing. Guidance on peripheral blood collection, processing and shipping is provided in Table 9.2 below.

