- O Gene expression signatures and somatic mutations: Tumor samples from the protocol surgery should be immersed in Allprotect tissue reagent solution (Qiagen) or RNA-later® reagent and shipped to the UCLA Brain Tumor Research Laboratory. Exome sequencing (tumor/PBMC) and RNA Seq will be performed at the UCLA GenoSeq Core facility and analyzed. We will assess the number of somatic mutations and potential neoantigens in each tumor using a new UCLA-developed pipeline (veraT) and this data will be correlated with clinical variables to identify potential biomarkers with prognostic and predictive value for outcomes (ORR, PFS, OS). We will also develop immune signatures with the sequencing data and evaluate whether the presence of a pre-existing immune signature can also be correlated with clinical variables.
- 4) Frozen tumor tissue from protocol surgery will be characterized using single-cell RNA-sequencing using the SMART-Seq2 protocol to analyze the transcriptional profile of tumor cells treated with abemaciclib, allowing us to identify differences in cellular programs in comparison to historical untreated controls. Single-cell suspensions from frozen will be sorted based on CD45 expression and markers of cell integrity and viability and sorted into 96-multiwell plates containing cell lysis buffer. We plan to bank 15 plates of CD45-negative (primarily malignant cells) and 5 plates of CD45+ (primarily immune) cells per specimen with this method.
- 5) FFPE tumor tissue from protocol surgery will be evaluated for tissue microenvironment using multiplexed IF. The goal is to determine the tumor's immunological state and the immune milieu of the tumor microenvironment with respect to MHC and other markers.
- 6) We will also perform additional novel PK determinations using Maldi Mass Spec methods developed by [name] (DFCI/BWH), which will be performed on frozen surgical specimens with excess tissue not needed for conventional methods of PK determination.
- 7) We will attempt to establish patient derived cells (PDC), cell lines/xenografts (PDCL/PDX) from patients on treatment with the goal to compare effects of abemaciclib on models to the patient response.

Cohort 1 Tumor Tissue Designation

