13. STATISTICAL CONSIDERATIONS

13.1 Study Design

This will be an open label Phase II trial in participants with recurrent GBM. Cohort 1 and Cohort 2 will enroll concurrently. In Cohort 1, to ensure that adequate abemaciclib penetrates into the tumors and inhibits cellular proliferation, 15 participants with recurrent GBM who require reoperation will be treated with abemaciclib prior to surgery. After recovery from surgery, participants will receive abemaciclib until disease progression or the development of unacceptable toxicities. In Cohort 2, participants will receive abemaciclib without undergoing prior surgery. The two cohorts will be analyzed separately.

In Cohort 1 we will attempt to characterize the pharmacokinetic (PK) uptake of abemaciclib in brain. A single-time point brain-to-plasma ratio will be calculated for each participant with a paired plasma and brain sample, followed by a descriptive statistical analysis (mean, SD, CV% or median (range)). In addition, both a naive pool strategy of all brain samples as well as a non-linear mixed effect approach will be explored in an attempt to provide a better estimate of time-course of brain uptake, the total brain exposure over a dosing interval (AUC0-24) and the brain-plasma tissue partitioning coefficient (Kpt).

Cohort 1 will also assess for pharmacodynamic (PD) evidence of target inhibition in brain tissue. We will evaluate tumor tissue after treatment with abemaciclib for reduced RB1 signaling,

cellular proliferation, and increased cell death by immunohistochemistry for pRB1, Ki67, and cleaved caspase 3. The IHC effects will be evaluated by pathologist manual scoring of each marker as well as morphometric techniques to determine change relative to pre-abemaciclib biopsy which will also be stained. These results will be compared to a group of 15 patient samples who received treatment only with standard of care TMZ and RT. Results of the two cohorts will be compared statistically to determine whether significant changes are noted.

The primary goal of Cohort 2 is to determine the therapeutic efficacy of abemaciclib as measured by PFS6. Treatment duration will be measured in 4-week cycles. Participants will remain on treatment until tumor progression, as long as there are no unacceptable toxicities. Responses will be assessed by clinical examinations every 4 weeks and MRI scans every 8 weeks.

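### Section 9.2 aims at predictive biomarkers in Cohort 1, where everyone receives abemaciclib, so a predictive effect cannot be separated from a prognostic one

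*Combined protocol and SAP*

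**What the plan says.** Section 9.2, under the immunological assays for Cohort 1, makes the statement twice. TIL density and TCR overlap are to be "correlated with clinical variables to identify potential biomarkers with prognostic and predictive value for outcomes (ORR, PFS, OS and toxicity". The paragraph on gene expression and somatic mutations says that mutation and neoantigen data will be used to "identify potential biomarkers with prognostic and predictive value for outcomes (ORR, PFS, OS", without toxicity, and adds immune signatures of unstated number.

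The cohort is described in Section 5.2: "In Cohort 1, 15-20 eligible participants who require reoperation will be treated with abemaciclib for 10-14 days prior to surgery". Section 1.1 describes the trial as open label, and there is no randomised or concurrent untreated arm. Section 13.1 adds: "The two cohorts will be analyzed separately". Untreated or standard-treatment specimens appear in Sections 1.4.1, 2.5, 9.2 and 13.1, but only as comparators for tissue assays.

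On treatment after surgery, Section 5.2 says "After surgery on study, cohort 1 participants will come off study treatment". It makes an exception for people enrolled before the phase 0 conversion who had already restarted the drug and were benefitting. Section 13.1 still has Cohort 1 resuming the drug after recovery from surgery.

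Section 1.4.1 lists this work as an exploratory objective and speaks only of associations. Section 13.4 also calls the detailed correlate analyses exploratory.

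**The concern.** A prognostic marker tracks outcome whatever the treatment. A predictive marker identifies people in whom the drug's effect is larger or smaller. Estimating the second requires outcomes with and without the drug at each marker level, and Cohort 1 supplies only outcomes with it.

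A correlation found here could therefore be reported as showing who benefits from abemaciclib when it shows only who does better or worse. The plan contains no criterion for telling the two apart. The practical risk is that a later trial selects or enriches on a marker that carries no information about the drug.

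**Working it through.** **1. Stated operating characteristics.** None is given for the biomarker analyses. The only such figures are for Cohort 2 in Section 13.3 (32 participants, success at 8 or more, 15% against 35%). Exact binomial calculation gives power 0.918 (stated 0.92) and a probability of rejection at 15% of 1 - 0.096 = 0.904 (stated 0.90). They reproduce, but do not bear on this point.

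**2. What can be estimated.** Let M be the marker and T = 1 if treated. Write the log hazard as a + bM + cT + dMT, where b is the prognostic effect and d the predictive one.
- In Cohort 1, T = 1 for everyone, so the log hazard is (a + c) + (b + d)M.
- Only the sum b + d is estimable. A hazard ratio of 2 between marker groups fits b = ln 2, d = 0 (purely prognostic) and b = 0, d = ln 2 (purely predictive) equally well. More participants do not help.
- Cohort 2 cannot fill the gap. It is also treated, and it is analysed separately.

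**3. When the markers are measured.** The tumour tissue comes from the protocol surgery, after 10-14 days of drug. TIL density and the expression signatures are thus on-treatment measures, which the drug may already have changed. They are not baseline characteristics.

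**4. Scale, if an untreated arm existed.** Assume 1:1 randomisation, an even marker split, 80% power and two-sided 0.05. Events needed for an interaction are 16 × (1.96 + 0.842)² / (ln R)², where R is the ratio of hazard ratios.
- R = 2: 16 × 7.85 / 0.480, about 262 events.
- R = 3: 16 × 7.85 / 1.207, about 105 events.
- Cohort 1 has at most 20 participants.

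**5. Precision of a simple association.** At two-sided 0.05, nominal significance needs |r| of at least 0.51 with 15 participants and 0.44 with 20. Power for a true r of 0.5 is 0.48 and 0.62.

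**6. Chance findings.** The documents state no alpha, test or number of tests. As an assumption, take 0.05 two-sided per pair, unadjusted, with no true effects.

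| Pairs | Independent | Correlated |
|---|---|---|
| TIL density, TCR overlap × 4 outcomes = 8 | 1 - 0.95⁸ = 0.34 | 0.29 to 0.21 (outcomes correlated 0.5 to 0.8) |
| The above + mutations, neoantigens × 3 outcomes = 14 | 1 - 0.95¹⁴ = 0.51 | just under 0.5 to 0.41 (ORR, PFS and OS correlated 0.5 to 0.8, toxicity independent); 0.43 to 0.36 if the paired markers also correlate at 0.5 and 0.9 |

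The correlated entries are simulations at 15 and 20 participants, and the correlations are assumed. Immune signatures would add to the count.

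**7. Which outcomes exist for phase 0 participants.**
- Section 3.1, item 10: the Cohort 1 screening scan is not used to evaluate response.
- Table 10.1: imaging at screening only, no required assessments after surgery, no long-term follow-up column. Section 5.6 describes long-term follow-up only for those who enter it.
- Sections 11.5 and 13.5: PFS and OS start at the first post-surgery dose, which these participants do not receive under Section 5.2.

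**The case against.** The strongest reply is that the plan claims little. The work is an exploratory objective, Section 1.4.1 speaks only of associations, Section 9.2 qualifies the biomarkers as potential, and Section 13.4 leaves the analysis open. With toxicity in the outcome list, predictive could loosely mean able to forecast an outcome. This stands as an argument about severity: no confirmatory conclusion or error rate is breached. It does not rescue the word. Section 9.2 names prognostic and predictive value as two separate things, and an exploratory label relaxes error control without making an inestimable effect estimable.

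A reader might infer more than the documents support:
- *That false positives are more likely than not.* The 0.51 needs 14 independent tests at an alpha the plan never states. The correlated cases in the table all fall below one half.
- *That a prognostic marker would pass the plan's test and be labelled predictive.* There is no test, threshold or decision rule, and the authors could call a finding prognostic. The fair statement is that nothing in the plan prevents the wrong label.
- *That every Cohort 1 participant stops the drug at surgery.* Section 5.2 has its exception and Section 13.1 says otherwise. Neither reading changes the conclusion: there is still no untreated group, and continuing the drug because of benefit adds selection.

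**Conclusion.** The point holds as a minor correction to a stated inference. Cohort 1 cannot identify predictive biomarkers, because the marker-by-treatment effect cannot be estimated in a cohort where everyone is treated. This follows from the design and needs no numerical assumption. Measuring tumour markers after drug exposure weakens the claim further.

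The false-positive ranges (0.21-0.34 for 8 pairs, 0.36-0.51 for 14) are illustrations under assumed unadjusted testing at 0.05. They support reporting how many pairs were examined, but not a finding that the plan fails to control error. Formal multiplicity control is a trade-off for exploratory work, and its absence is not a fault by itself.

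**What to change.** In both paragraphs of Section 9.2, delete the word predictive. State that the results are hypothesis-generating associations in abemaciclib-treated participants and cannot show differential benefit, which brings the text into line with objective 1.4.1. Report estimates with confidence intervals and the number of marker-outcome pairs examined.

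Two related repairs belong in the same edit. Limit the analyses to outcomes actually collected for phase 0 participants. Reconcile Sections 5.2 and 13.1 on whether Cohort 1 receives the drug after surgery.

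The cost is wording and light reporting, with no new data. The downside is a weaker biomarker claim.

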1.4 Exploratory Objectives

1.4.1 Cohort 1

- To investigate associations between clinical outcomes and immunologic effects of abemaciclib including quantitative assessments of tumor infiltrating lymphocytes (TIL) that express PD-1, delineation of PD-L1+ cells in the tumor microenvironment, assessment of immune pathways pretreatment and posttreatment, and quantitative assessment of T cell receptors from tumor samples pretreatment and posttreatment.
- To investigate the effects of abemaciclib on cellular programs as characterized using single-cell RNA-sequencing based on tumor samples posttreatment in comparison to historical untreated controls.
- To investigate the effects of abemaciclib on tumoral antigen presentation and the immune milieu of the tumor microenvironment based on tumor samples posttreatment in comparison to historical untreated controls.
- To investigate the effects of abemaciclib on patient-derived cells (PDC), cell lines (PDCL) and xenografts (PDX) established from patients on the study.

1.4.2 Cohort 2

- To correlate response to treatment with molecular phenotype of pre-treatment tumor (Oncopanel sequencing and array CGH copy number analysis);
- To investigate the mechanisms of resistance to abemaciclib by examining tumor tissue obtained from patients who progress on treatment, when available, with pretreatment tumor.

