2.5 Correlative Studies Background

Cohort 1: In this cohort, patients with recurrent GBM will receive drug for 10-14 days prior to a reoperation. Tumor will be resected and analyzed for:

- 1) Pre-treatment tumor will be genotyped with next generation sequencing and the results correlated with outcome if not previously performed.
- 2) Drug concentration using liquid chromatography tandem mass spectrometry (LC-MS/MS). Tumor concentration will be compared to plasma drug concentrations to determine if therapeutic levels of abemaciclib can be achieved in both enhancing and non-enhancing tumor.
- 3) Tumor tissue will be analyzed by IHC and proteomics analysis for Phospho-Rb, (S807/811) proliferation (Ki-67), and apoptosis (cleaved caspase 3) to determine if abemaciclib can achieve a pharmacodynamic effect in enhancing and non-enhancing tumor tissue. These data will be compared to results from the patient's prior archived tumor tissue not exposed to abemaciclib obtained from each participant's prior surgery, and to results from unrelated glioblastoma patients (n=10) with tumor tissue from preand post-treatment with standard of care RT+TMZ.
- 4) Tumor tissue will be analyzed for quantitative assessment of TIL that express PD-1, delineation of PD-L1+ cells in the tumor microenvironment (macrophage vs. tumor cells), immune response based multiplex gene expression analysis in tumor samples preand post-treatment, and quantitative assessment of T cell receptors in tumor samples preand post-treatment
- 5) Tumor tissue will be analyzed for tumoral expression of major histocompatibility complex type I and II, markers of T-cell exhaustion, type III interferon production and profiling of the immune milieu of the tumor microenvironment by multiplexed immunofluorescence (IF), and activation of abemaciclib-induced intrinsic anti-tumor immunity by gene expression analysis.
- 6) If sufficient tumor is available, fresh patient derived cells (PDC), patient-derived cell lines (PDCL), and patient derived xenografts (PDX) will be attempted to be generated.
- 7) Fresh cells or PDCL/PDX models will undergo functional sensitivity testing to abemaciclib or studied using genomics or expression analysis.

Cohort 2: Tumor from the participant's surgery prior to enrolling onto the study will be studied for correlative markers.

- 1) Pre-treatment tumor will be genotyped with next generation sequencing and the results correlated with outcome if not previously performed.

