UCLA)				Pre-surgery post treatment blood:10 Green top	[contact]
				tubes (10ml – sodium heparin tubes preferred)	
				prior to abemaciclib dosing on the morning of	

				surgery	
Gene expression signatures and somatic mutations ([name] / [name] / [name], UCLA)	Cohort 1	RNA Seq on tumor gDNA/RNA	Fresh preserved tissue from protocol surgery and peripheral blood (pre- and post-treatment)	The protocol surgery sample labeled 5 (CE-IM). collected for TIL Density and TCR Overlap will also be used for gene expression signatures and somatic mutations. Pre-treatment and post-treatment PBMC can be used from blood collected for peripheral blood immunophenotyping (see above).	[name]. C/O [name] [name] [name] [contact]
Single-cell RNA- sequencing ([name], MGH)	Cohort 1	Single-cell RNA- sequencing (SMART-Seq2)	Frozen tissue from protocol surgery	Protocol surgery: 200mg of fresh frozen tissue (frozen on dry ice, no OCT, no LN2) < 3 hours from surgery, obtained from the contrast enhancing region and placed into an individual cryovial labeled 6 (CE-RNA). Freeze the tumor specimen (frozen on dry ice , no OCT, no LN2). 200 mg (~0.5cm³) of tissue.	[name] (attn.: Adult Path CRC) Dana-Farber Cancer Institute Center for Molecular Oncologic Pathology - JF215B [name] [contact]
Cell line studies ([name], DFCI)	Cohort 1	Dynamic response to abemaciclib in vitro	Cell line derived from protocol surgery	Protocol surgery: 200mg or more tissue should be sent fresh to the local hospital research lab for establishment of a participant primary cell line (serum free, neurosphere methods) by the site's standard procedures. For sites that create cell lines locally the central site (DFCI, [name]) will request frozen aliquot of live cells in DMSO – if available – at a later date (may be ~ 6 months after surgery); but this is not a mandated study submission. If the local site does not have capability or would prefer the fresh tissue can be submitted in RMPI media to [name] lab for culture instead of the local site. This should be shipped at 4 degrees on wet ice.	[name] (attn.: Adult Path CRC) Dana-Farber Cancer Institute Center for Molecular Oncologic Pathology - JF215B [name] Ph [contact]

Cohort 1 Blood Samples for Peripheral Blood Immunophenotyping:

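### Cohort 1's before/after tumor comparison of T-cell receptors and immune gene expression has no pre-drug tumor assigned to it, and the 'pre-existing' immune signature would come from drug-exposed tissue

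*Combined protocol and SAP*

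**What the plan says.** Two places state the aim. The Cohort 1 exploratory objectives (section 1.4.1) include "assessment of immune pathways pretreatment and posttreatment" and "quantitative assessment of T cell receptors from tumor samples pretreatment and posttreatment". Section 2.5, item 4, repeats the T-cell receptor aim and names tumor as the specimen for expression as well: "immune response based multiplex gene expression analysis in tumor samples preand post-treatment".

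Section 9.2 and Table 9.2 say which tissue is used:

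- **TCR sequencing.** "Genomic DNA will be isolated from fresh-frozen tumor (protocol surgery) and peripheral blood (immune monitoring timepoints". Table 9.2 identifies the tumor sample as tube 5 (CE-IM).
- **RNA-Seq and exome sequencing.** "Tumor samples from the protocol surgery should be immersed in Allprotect tissue reagent solution". The specimen entry in Table 9.2 reads "Fresh preserved tissue from protocol surgery and peripheral blood (pre- and post-treatment", and the collection entry says the tube 5 sample "collected for TIL Density and TCR Overlap will also be used for gene expression signatures and somatic mutations".
- **Use of the result.** Signatures are to be built from the sequencing data, and the investigators will then "evaluate whether the presence of a pre-existing immune signature can also be correlated with clinical variables".

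Sections 5.2 and 9.2 place the protocol surgery after 10-14 days of abemaciclib, with the last dose 1-3 hours before surgery and tumor removal.

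**The concern.** The stated aim and the assigned specimens do not match. A before/after comparison in tumor needs tumor from both times, and these assays list tumor from one time only.

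The label on the signature adds to the problem. A signature called pre-existing will be read as a feature the tumor had before abemaciclib. Yet section 2.4 gives the trial's own hypothesis that CDK4/6 inhibition raises tumor antigen presentation and suppresses regulatory T cells. If that is right, 10-14 days of drug can change what an immune signature measures. A correlation with clinical variables would then mix what the patient brought to the trial with how the tumor responded to the drug, while the report called it baseline.

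**Working it through.** No alpha, power or sample-size figure is involved. The check is to trace each specimen to its assay.

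| Cohort 1 assay | Tumor before drug | Tumor after drug | Other comparator in the plan |
|---|---|---|---|
| TCR sequencing | none assigned | tube 5 | blood, before and after |
| RNA-Seq / immune signature | none assigned | tube 5 (same tube) | blood cells from both times may be used |
| Exome sequencing | none assigned | tube 5 (same tube) | blood cells from both times may be used |
| PD-1/PD-L1 multiplex immunofluorescence | archival slides | protocol-surgery slides | – |
| Pharmacodynamic IHC (pRb, Ki-67, cleaved caspase 3) | archival slides | protocol-surgery slides | external glioblastoma samples |
| Single-cell RNA-seq | none | tube 6 | historical untreated controls |
| OncoPanel and array CGH (section 9.2.1) | prior-surgery tissue | protocol-surgery tissue | – |

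**Step 1: which samples the before/after label covers.** The Table 9.2 rows for TCR and for gene expression each list one tumor collection, the protocol surgery, and two blood collections. The words pre- and post-treatment in those rows can therefore apply only to the blood.

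**Step 2: where the archival tumor goes.** Table 9.2 sends 20 archived slides to DFCI for IHC and multiplex immunofluorescence, and 7 to UCLA for multiplex immunofluorescence. Section 9.2.1 describes genotyping of prior-surgery tissue, but by DNA assays that give neither an expression signature nor a TCR repertoire. No section assigns archival tumor to RNA-Seq or TCR sequencing.

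**Step 3: count.** Tumor pairs per participant = the smaller of (pre-drug samples, post-drug samples) = the smaller of (0, 1) = 0. Over 15 planned participants, 15 × 0 = 0 pairs. At the enrollment ceiling of 20 the answer is still 0.

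**Step 4: the signature.** The only tumor in the RNA-Seq row is tube 5, and the assay column of Table 9.2 names tumor nucleic acid. A signature built from it is measured after exposure in every participant, with no unexposed tumor in the same assay to show which part was there before.

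**Step 5: what follows for each assay.** For the signature, drug effect can be mislabelled as baseline. For TCR, section 9.2 introduces the immune assays as tests of the drug's own immunostimulatory effect, so the tissue is already treated as drug-exposed. The only consequence is that the tumor comparison promised in 1.4.1 and 2.5 cannot be made from the assigned samples.

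**The case against.** The strongest reply is that this is loose wording in exploratory text. Section 13.4 calls the detailed correlative analyses exploratory and dependent on the data obtained, and section 9.2 lets the sponsor drop assays. Archival FFPE is required at eligibility, section 9.2 lists archival slides among the samples for immunologic assays, and nothing forbids running RNA or TCR on them. The gene-expression row also lists pre-treatment blood cells, so the origin of the signature could be called ambiguous.

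Much of this stands. The tissue is unassigned rather than unobtainable, and the aims carry no formal test. But the only use Table 9.2 gives the UCLA archival slides is multiplex immunofluorescence, and blood cannot supply a baseline tumor signature or tumor repertoire. If pre-existing was meant in some other sense, the text still needs to say so.

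A reader might also infer four stronger things that the documents do not support:

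- *The signature is put forward as a prognostic and predictive marker.* In the gene-expression paragraph of 9.2 that language attaches to somatic mutations and neoantigens, and in the TCR paragraph to TIL density and TCR overlap. The signature sentence speaks only of correlation.
- *The TCR data would also be read as baseline.* Section 9.2 presents them as tracking responses induced by abemaciclib.
- *The immune question of the Phase 0 amendment cannot be answered.* Section 2.4 gives two reasons for keeping the surgical cohort, the other being why activity was limited, and states the purpose as tissue PK and PD. Several immune assays have comparators of their own, as the table in the working shows.
- *An on-treatment signature should not be related to outcome at all.* That analysis is legitimate if it is labelled for what it is.

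**Conclusion.** The point holds, within limits. For TCR sequencing and RNA-Seq the plan promises a tumor comparison for which 0 of 15 participants would have the assigned samples. It also attaches a baseline label to a signature that, on those samples, would come only from drug-exposed tumor. The mislabelling applies to the signature; for TCR the defect is an unmet comparison.

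This rests on two assumptions: that Table 9.2 and the section 9.2 text are the full specimen allocation, and that the signature is derived from the tumor RNA-Seq listed there. How far abemaciclib shifts such a signature is not given in the documents. The concern needs only the possibility, which section 2.4 itself raises. No primary or secondary endpoint and no safety decision is touched. Priority is low, but the correction is cheap and changes what the immune results can be said to show.

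**What to change.** 1. In section 9.2, call it an on-treatment immune signature. State that any correlation with outcome from protocol-surgery tumor, including TIL density and TCR overlap, is reported as on-treatment and not as baseline.
2. In sections 1.4.1 and 2.5 (item 4), describe tumor TCR and tumor RNA as post-treatment only. Keep the before/after comparison in blood for TCR and in tumor for multiplex immunofluorescence.
3. If the sponsor prefers to keep the tumor before/after objective, replace step 2 with an explicit assignment in Table 9.2 of the archival FFPE already collected to the TCR and RNA assays, and limit the on-treatment label in step 1 to results from protocol-surgery tissue. State the limits:
   - Cohort 1 archival tissue may come from any prior surgery, so time and intervening therapy differ between the paired samples.
   - Archival tissue is FFPE while tube 5 is fresh-preserved. Protocol-surgery FFPE should be run alongside, so that preservation method does not coincide with treatment.
   - The number of spare sections must be confirmed. Table 9.2 asks for 20 archived slides at DFCI while section 9.2.3 accounts for 10, so what remains is not settled.

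The wording route costs only an edit to three sections and a narrower exploratory claim. The archival route costs additional assays and an imperfect baseline.
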